### 14.3.2 DB Inclusion/Exclusion for NH

Subjects from the NH were selected to reflect the baseline criterion of the CPI-IFE007 study before the propensity score is calculated. The following criteria will be applied for matching with the DB subjects given the High dose:

- Male subjects  $\geq$  7 years old.

- 2 years data of LVEF.
- Baseline value LVEF of  $\geq 35\%$  (baseline is pre-dose in study)
- No current treatment with givinostat (Duvyzyat®), empagliflozin (Jardiance®), dapagliflozin (Farxiga®), canagliflozin (Invokana®) (Variables: other\_meds\_listed ≠ “givinostat,” “emplagliflozin,” “dapagliflozin,” “canaglifloxin,” “duvyzyat,” “Jardiance,” “farxiga,” “Invokana”)
- Corticosteroids Stable Dose (Stable dose for  $\geq 56$  of corticosteroids days or no corticosteroids for  $< 30$  days prior to the start of baseline).
- Subjects with no history of heart failure.
- Live subjects with non-missing cardiac efficacy data (CFB LVEF and CFB Myocardial strain) at baseline and month 12
- Patients given High dose in DB

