7.3.2 Exclusion Criteria

Individuals who meet any of these criteria are not eligible for enrollment as study subjects:

1. Clinically significant illness other than DMD
2. Clinically significant laboratory abnormality not associated with DMD
3. Major surgery within six weeks prior to the first dose of study drug, or planned surgery during this study which would interfere with the ability to perform study procedures
4. Require antiarrhythmic therapy and/or initiation of diuretic therapy for management of acute heart failure in the last 6 months
5. A LVEF of < 35% by CMR and/or fractional shortening of < 15% based on (ECHO during screening
6. A known bleeding disorder or has received anticoagulant treatment within two weeks of study entry

7. Allergy to gadolinium contrast or known renal insufficiency defined as abnormal cystatin C or creatinine above the upper limit of normal for age. The male serum reference ranges as follows:
 - Age 7-9 years - 0.2 - 0.6 mg/dL
 - Age 10-11 years - 0.3 - 0.7 mg/dL
 - Age 12-13 years - 0.4 - 0.8 mg/dL
 - Age 14-15 years - 0.5 - 0.9 mg/dL
 - Age 16 years or older - 0.8 - 1.3 mg/dL
8. Non-MR compatible implants (e.g. neurostimulator, automatic implantable cardioverter-defibrillator [AICD])
9. Subjects who participated in a therapeutic clinical trial within 30 days or five half-lives (whichever is longer) of study entry
10. Any other condition that could interfere with the subject's participation

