7.5 Prohibited Medications and Procedures

Before enrollment, a medication history will be collected for each subject to ensure that no prohibited medications will be taken during the study and no surgeries or prohibited procedures are planned. The following medications and procedures are prohibited throughout the study:

- Major surgery within six weeks prior to the first dose of study drug, or planned surgery during this study which would interfere with the ability to perform study procedures
- Use of warfarin or any other antiplatelet or anticoagulant medications in the last two weeks before starting treatment
- Any investigational therapy for DMD
- Any concomitant medication with a depressive or stimulating effect on respiration or the respiratory tract.

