11.5 Historical Comparator

Data collected from an FDA-funded DMD NHS will be used as a historical comparator/supplemental placebo group ([Soslow 2023](#)). The NHS utilized as a comparator is an ongoing, multi-year, multicenter study evaluating the natural progression of DMD. Eligibility is broad based on DMD diagnosis, and endpoints collected mirror endpoints collected for CPI-IFE-007 except patient-reported outcomes (PedsQL). NHS visits are scheduled yearly, and demographic, baseline characteristics, medical history, and concomitant medication information is collected at each visit along with CMR, PFTs, QMT, and accelerometry. Patients from the NHS will be selected at a 2:1 ratio (NHS to placebo) using propensity score matching (PSM) based on baselined LVEF, age, and background DMD therapy with consideration for other relevant cardiac medications (ACEi, ARB, beta-blockers, ARNI, aldosterone receptor antagonists, diuretics, calcium channel blockers. Matched NHS patients will be added to the CPI-IFE-007 placebo group from the 12-month double-blind study to create a supplemental, representative placebo group of a larger size for Month 12 efficacy analyses. For the open label extension, a historical comparator group will be formed from NHS patients selected at a 2:1 ratio (NHS to open label high-dose ifetroban) using PSM as described above. The NHS comparator group for the open label extension will be compared with open-label high-dose ifetroban patients at Month 12, Month 24, and Month 36.

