#### **14.3.3 OL Matching Inclusion/Exclusion for NH**

Subjects from the NH were selected to reflect the baseline criterion of the CPI-IFE007 study before the propensity score is calculated. The following criteria were applied for matching with the OL subjects:

- Male subjects  $\geq 7$  years old.
- 2 years data of LVEF
- Baseline value LVEF of  $\geq 35\%$  (baseline is month 12 in study)
- Subjects with no history of heart failure.
- No current treatment with givinostat (Duvyzyat®) (Variables: other\_meds\_listed ≠ “givinostat,” “duvyzyat”)
- Live subjects with non-missing cardiac efficacy data (CFB LVEF and CFB Myocardial strain) at baseline and month 12 for OL. Live subjects with non-missing cardiac efficacy data (LVEF and Myocardial strain) at month 12 and month 24 for OL. Missing data will not be imputed.

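### The natural-history control lists omit the trial's bars on other trials and investigational drugs, and do not exclude boys also in CPI-IFE-007, so ifetroban-exposed or duplicate boys can enter the comparator

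*SAP*

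**What the plan says.** SAP 14.3.2 (double-blind) and 14.3.3 (open-label) list the conditions an NHS subject must meet before propensity scores are computed. The stated aim is: "Subjects from the NH were selected to reflect the baseline criterion of the CPI-IFE007 study before the propensity score is calculated". SAP 14.3.1 presents the result as a comparison of ifetroban-treated with untreated subjects.

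The drug screens name products only. The double-blind item opens "No current treatment with givinostat" and adds three SGLT2 inhibitors; the open-label list names givinostat alone. Both lists require "2 years data of LVEF". The double-blind list also requires "Live subjects with non-missing cardiac efficacy data (CFB LVEF and CFB Myocardial strain) at baseline and month 12", and the open-label list has a parallel item for its own visits.

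The trial applies two further rules to its own subjects. Protocol 7.3.2 excludes "Subjects who participated in a therapeutic clinical trial within 30 days or five half-lives (whichever is longer) of study entry". Protocol 7.5 prohibits "Any investigational therapy for DMD".

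On the source of controls, Protocol 11.5 says: "The NHS utilized as a comparator is an ongoing, multi-year, multicenter study evaluating the natural progression of DMD". It describes NHS eligibility as broad. The protocol synopsis makes the NHS the primary comparator for the open-label extension. SAP 4.5.3 labels the NHS comparisons supplementary beside the randomised double-blind comparison.

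**The concern.** The lists are meant to make NHS controls look like trial subjects at entry and to keep them untreated. Applied as written, they admit an NHS interval during which a boy was taking another study drug, or ifetroban itself within CPI-IFE-007. They also admit an earlier, untreated NHS interval from a boy who later appears in the trial arms.

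Three consequences differ in kind:

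- **Ifetroban-exposed controls** carry part of the drug effect and pull the contrast towards zero.
- **Controls on other investigational drugs** can shift the comparator in either direction.
- **Duplicate boys** break the independence of the two samples that the Wilcoxon rank sum test assumes. A boy may stand on both sides, or a placebo boy may be counted twice in the pooled control group.

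Most is at stake in the extension, which has no concurrent randomised control.

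**Working it through.** **Rules side by side**

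| Condition | Trial subjects | NHS, double-blind list | NHS, open-label list |
|---|---|---|---|
| Recent therapeutic-trial participation | Excluded (Protocol 7.3.2) | Not mentioned | Not mentioned |
| Investigational DMD therapy | Prohibited (Protocol 7.5) | Four named drugs only | Givinostat only |
| Also enrolled in CPI-IFE-007 | – | Not mentioned | Not mentioned |

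**Can the same boy be in both studies?** The NHS is running alongside the trial, is multicentre and takes a broad DMD population. The trial's own exclusion concerns therapeutic trials, so belonging to a natural-history study does not bar entry. Neither document calls for an identity check between the datasets.

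**Does anything later remove him?** The propensity covariates (SAP 4.5.1 and 14.3.4) are age, LVEF, background DMD drugs and cardiac drugs; none records trial exposure. Matching without replacement (SAP 4.5.2) stops an NHS record being used twice, but not a boy appearing once in each dataset. An NHS record close to a boy's trial baseline would have nearly the same covariates, hence nearly the same score, so nearest-neighbour matching would tend to pick it. The unmatched sensitivity analysis in SAP 14.3.8 uses the eligible NHS cohort. The weighting, caliper and exact-matching analyses state no separate eligibility rule. All start from the same pool.

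**Size.** The plan gives no overlap figure to reproduce, so this is a range under assumptions. Let δ be the true mean difference, n the number of controls and k the number exposed to ifetroban, each assumed to carry the full effect. The control mean moves by δ·k/n, so the observed contrast is δ(1 − k/n) and the proportional loss is k/n.

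Inputs: 16 subjects per arm (8 early plus 8 advanced; Protocol 7.1), 48 in total, and NHS matching at 2:1 (SAP 4.5.2).

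| Comparison | n | k = 2 | k = 4 | k = 8 |
|---|---|---|---|---|
| High-to-high vs NHS only, if all 16 continue | 2 × 16 = 32 | 6% | 13% | 25% |
| Double-blind: placebo plus NHS | 16 + 32 = 48 | 4% | 8% | 17% |
| All open-label vs NHS, if all 48 enter | 2 × 48 = 96 | 2% | 4% | 8% |

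SAP 14.3.1 can also be read as 2:1 for the whole double-blind control group. That gives 16 placebo plus 16 NHS, so the middle row would use n = 32.

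**Power, as an illustration.** Simulated Wilcoxon tests (20,000 trials, normal data, SD 1) compared 16 high-dose subjects with 16 placebo plus 32 NHS controls. With δ = 0.8 SD, half the planning effect of 1.6, power is 75.1% with no exposed controls, 67.3% with 4 and 58.2% with 8. With δ = 1.6 SD it stays above 99% in all three cases.

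**The case against.** The strongest reply is that no overlap is documented. The SAP intends untreated controls, the NHS records medication at each visit, and dataset specifications sit in separate documents (SAP 10) that may contain the exclusion. This stands as far as it goes: nothing shows that any boy is in both studies. But the SAP sets out an explicit eligibility list with a stated aim, and a description of controls as untreated does not work as a selection rule.

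The second reply is that ifetroban exposure among controls is conservative. That also stands. With no drug effect, such dilution produces no false positive. It does not cover other trial drugs or the loss of independence.

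Third, the double-blind NHS analysis is supplementary, so the gap there leaves the randomised comparison untouched. This is correct, and it is why the weight falls on the extension.

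A reader might go further and infer from the word *live* and the two-year LVEF requirement that the controls are survivors only. The documents do not support that. *Live* sits in an item tied to the baseline and Month 12 visits. With yearly NHS visits, two years of data may mean just two annual assessments. Completeness is also imposed on trial subjects: SAP 14.3.6 restricts the double-blind arms to those evaluable at Month 12, and SAP 4.2 drops open-label subjects missing key timepoints. A Baseline-to-Month-24 analysis (SAP 6.4.1) legitimately needs two years of data. What remains is an ambiguity to clear up.

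**Conclusion.** The omission is confirmed from the text. Neither NHS list carries over the trial's rules on recent therapeutic trials and investigational DMD therapy, and neither excludes boys who are also in CPI-IFE-007. The comparator can therefore contain ifetroban-exposed, otherwise treated or duplicate boys; whether it does is unknown.

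For 2 to 8 ifetroban-exposed controls the contrast loses 6–25%, 4–17% or 2–8%, depending on the comparison. These figures assume full exposure effect, complete arms and 2:1 matching. The direction is towards hiding benefit. Bias from other trial drugs has no fixed direction, and the effect of duplicates on the test is not quantified here. The change should be made, chiefly because the protocol makes the NHS the primary comparator for the extension.

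The *live* and two-year items are a secondary point of wording, and no size is attached to them.

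**What to change.** Add to both SAP 14.3.2 and 14.3.3:

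1. Exclude any NHS interval that overlaps participation in CPI-IFE-007 or another interventional DMD trial, applying the window the protocol already uses in 7.3.2 (30 days or five half-lives, the longer).
2. Exclude any NHS patient also randomised in CPI-IFE-007.
3. Check both by an identity cross-match with the NHS data holder before propensity scores are estimated, and report how many patients and intervals are removed.

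As a clarification, tie the *live* and two-year LVEF items to the interval compared: baseline and Month 12 for the double-blind analysis; Month 12 and Month 24, or baseline and Month 24, for the open-label analyses. Controls are then not screened on events after that interval. Apply the same completeness rule to trial subjects. Reconcile this with SAP 14.3.1, which says NHS subjects with non-missing cardiac data are left out of matching, the opposite of what 14.3.2 requires.

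The cost is a few SAP lines, one linkage query and a slightly smaller pool. Limiting the analysis to boys assessed at both ends of the interval still makes it a comparison among completers, and the report should say so.

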7.4 Concomitant Medications

A concomitant medication is any treatment received by the subject concomitantly to the IMP. All concomitant medication use will be tracked in the subject diary and recorded in the appropriate Case Report Form (CRF).

The following concomitant medications are allowed:

- ACEI, BB, and ARB therapies are allowed (selection of which dictated by clinical care) if started three months or greater from start of IMP treatment with no change in dose and no changes throughout the study, except in the event of a decline in left ventricular ejection fraction (LVEF) >5% following the baseline CMR as measured by a subsequent CMR at the same center. Should this occur, changes in cardiac medications are allowed on study, and the patient may remain on IMP.
- Aldosterone receptor antagonists (e.g. spironolactone or eplerenone) allowed if started 12 months or greater from first dose of IMP. No changes allowed throughout the study, except in the event of a decline in left ventricular ejection fraction (LVEF) >5% following the baseline CMR as measured by a subsequent CMR at the same center. Should this occur, changes in cardiac medications are allowed on study, and the patient may remain on IMP.

- Oral corticosteroids are allowed if started at least 8 weeks or greater from start of IMP treatment with no change in dose and no changes throughout the study. If not currently on oral corticosteroid, the subject must not have received corticosteroids for at least 30 days from the start of IMP treatment.
- Diuretics are allowed if there has not been an adjustment in dosing for 6 months (e.g. furosemide or equivalent)
- FDA-approved antisense oligonucleotide (ASO) therapy for DMD: Eteplirsen, Golodirsen, Casimersen, and Viltolarsen
- During the open-label extension period, use of givinostat, an FDA-approved therapy for DMD, is permitted. Changes to cardiac medications or the administration of additional cardiac medications, including angiotensin receptor/neprilysin inhibitors (ARNI) and sodium glucose cotransporter-2 (SGLT2) inhibitors, are permitted during the OLE.

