#### **14.3.4 List of Baseline Covariates for Modeling**

The following baseline covariates will be included in the DB and OL Model to create the propensity score.

- Age
- Baseline left ventricular ejection fraction (LVEF). Baseline will represent pre-treatment values in DB and Month 12 visit values will be the baseline in the OL study.
- Background DMD medications (current steroids, Current ASO/exon skipping)
- Additional cardiac medications (Aldosterone antagonists, Beta-blocker, ACEi, ARB, Calcium channel blockers, ARNI)

The following chart will be used to define the baseline med covariates in the NH dataset.

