**Table 1 Background DMD Therapies and Cardiac Medications of Relevance by Class**

Med Type (Natural Data Variable name)	Definition of Generic (Brand Name)
ASO/Exon skipping therapy (aso_yn)	Exondys 51 (eteplirsen) Amondys 45 (casimersen) Viltepso (viltolarsen) Vyondys 53 (golodirsen)
Aldosterone antagonists ( aldosterone_yn)	Eplerenone (Inspra) Finerenone Spironolactone (Aldactone/CaroSpir)
Beta-blocker (bb_yn)	Acebutolol Atenolol (Tenormin) Bisoprolol Metoprolol (Lopressor, Toprol XL) Nadolol (Corgard) Nebivolol (Bystolic) Propranolol (Inderal LA, InnoPran XL) Carvedilol (Coreg)
ACEi /angiotensin converting enzyme inhibitor (taking_ace )	Benazepril (Lotensin) Captopril Enalapril (Vasotec) Fosinopril Lisinopril (Zestril) Moexipril

Med Type (Natural Data Variable name)	Definition of Generic (Brand Name)
	Perindopril Quinapril Ramipril (Altace) Trandolapril
ARB /angiotensin receptor blocker (ARB_YN)	Azilsartan (Edarbi) Candesartan (Atacand) Irbesartan (Avapro) Losartan (Cozaar) Olmesartan (Benicar) Telmisartan (Micardis) Valsartan (Diovan)
Calcium channel blockers (cach_yn)	Amlodipine (Norvasc) Diltiazem (Cardizem, Tiazac) Felodipine (Plendil) Nifedipine (Procardia) Nisoldipine (Sular) Verapamil (Calan, Isoptin, Tarka, Verelan)
Steroids (new_med_steroid_v1— new_med_steroid_V.., steroid_change_type, start_date_steroid )	Prednisone/prednisolone Hydrocortisone (note that hydrocortisone cannot be the cream) Deflazacort (Emflaza) Deflazcort Deflazocort Emflaza Emflaza-Delfazacort Solu-Cortf Agamree/vamorolone
ARNI/angiotensin receptor/neprilysin inhibitor (ARNI_yn)	Sacubitril/Valsartan (Entresto)

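### The rule that screens natural-history controls for SGLT2 inhibitors misspells two of the three generic names, so users recorded under those names may remain eligible for double-blind matching if it is coded as written

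*SAP*

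**What the plan says.** SAP 14.3.2 lists the criteria a natural-history (NH) subject must meet before the double-blind (DB) propensity score is calculated. One of them reads "No current treatment with givinostat (Duvyzyat®), empagliflozin (Jardiance®), dapagliflozin (Farxiga®), canagliflozin (Invokana", followed by the variable rule in brackets. That rule names the field `other_meds_listed`, uses a not-equal sign and gives eight strings: givinostat, three SGLT2 generic names and four brand names. The SGLT2 generic strings are "emplagliflozin,” “dapagliflozin,” “canaglifloxin". The brand strings are "duvyzyat,” “Jardiance,” “farxiga,” “Invokana".

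The propensity model in SAP 14.3.4 covers age, baseline LVEF, background DMD medication and "Additional cardiac medications (Aldosterone antagonists, Beta-blocker, ACEi, ARB, Calcium channel blockers, ARNI". SAP 4.5.1 adds diuretics. Neither list contains SGLT2 inhibitors, and SAP Table 1 defines no SGLT2 class.

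Table 1 does list spelling variants for steroids: "Deflazcort Deflazocort Emflaza Emflaza-Delfazacort Solu-Cortf". The correct spelling, deflazacort, stands beside them in the same cell.

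**The concern.** The sponsor has decided that a DB control should not be on one of these drugs. The rule meant to carry out that decision does not match two of the three SGLT2 generic names it is supposed to find. If it is coded as written, a subject recorded as taking empagliflozin or canagliflozin passes the screen.

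At stake is the composition of the NH-supplemented placebo group in the Month 12 comparison of LVEF and myocardial strain. The direction of any bias is not known. A cardiac benefit of the drug in controls would hide an ifetroban effect. Prescribing to patients whose hearts are already declining would exaggerate one.

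**Working it through.** No sample size or power figure enters this point. The check compares the names in the prose of SAP 14.3.2 with the strings in the rule that follows.

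| Name in the prose | String in the rule | Exact match | Ignoring case | String contained in the entry, ignoring case |
|---|---|---|---|---|
| givinostat | givinostat | yes | yes | yes |
| empagliflozin | emplagliflozin | **no** | **no** | **no** |
| dapagliflozin | dapagliflozin | yes | yes | yes |
| canagliflozin | canaglifloxin | **no** | **no** | **no** |

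Each failing string is one edit away from the correct name: an inserted l in the first, x for z in the second. No other string in the rule matches either correct name. The rule therefore catches 1 of 3 SGLT2 generic names. With the two strings spelled as in the prose, it catches 3 of 3.

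The four brand names are spelled correctly and are all caught when case is ignored. A user recorded only as Jardiance or Invokana would then be screened out.

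**Does a later step catch the retained subjects?**

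1. *Propensity model (SAP 4.5.1 and 14.3.4).* SGLT2 use is not a covariate, so matching does not balance it.
2. *Matching (SAP 4.5.2).* NH subjects are matched 2:1 to high-dose subjects without a caliper. A retained subject may be selected or not.
3. *Sensitivity analyses (SAP 14.3.8).* The inverse-probability-weighted analysis and the comparison with the entire eligible NH cohort start from the same eligible pool. The whole-cohort comparison promises covariate adjustment but does not name the covariates. Neither can be relied on to reveal the error.

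**What one retained and matched subject would weigh.** Protocol Table 7-1 plans 8 + 8 = 16 high-dose and 8 + 8 = 16 placebo subjects. Matching 2:1 as in SAP 4.5.2 gives 2 × 16 = 32 NH controls and a supplemented comparator of 32 + 16 = 48. One such subject is 1/32 = 3.1% of the NH part and 1/48 = 2.1% of the comparator. These are planned counts. SAP 14.3.6 restricts the analysis to subjects with evaluable Month 12 data, so the actual shares may be somewhat larger. The documents do not say how many NH subjects take these drugs.

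**The case against.** The strongest reply is that this is a typing slip in a bracketed pointer. The criterion is the prose, which is correct. A not-equal sign followed by eight strings is shorthand rather than executable code, and SAP section 10 places the programming rules in separate documents that are not available here. A programmer who follows the prose, or codes the drugs first, avoids the error. This stands as a limit: whether the misspelling reaches any program is unknown. It does not remove the mismatch between criterion and rule.

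A second reply is that the odd spellings may be copied from the NH data, as the steroid variants in Table 1 may be. That is possible. But Table 1 keeps the correct spelling beside its variants and the rule in 14.3.2 does not, so correctly recorded users would still pass.

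A third reply concerns consequence. SAP 4.5.3 labels the NH comparisons supplementary to the randomised ones, and the primary endpoint is safety. The same list in 14.3.2 requires no history of heart failure, and baseline LVEF is in the propensity model. Both limit the route by which sicker patients would bias the result. All of this stands.

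A reader might also infer more than the documents support:

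- *That SGLT2 users are in the control group.* They would remain eligible. They enter the matched group only if they exist, are recorded under one of the two generic names, and are selected.
- *That nobody could notice them.* SAP 14.3.7 plans baseline summaries by group that include concomitant medication use, although no SGLT2 class is defined for them.
- *That brand names are missed because of mixed capitals, or that entries naming two drugs slip through.* Both depend on matching behaviour and a field structure that the SAP does not state.
- *That the open-label matching has the same fault.* Its rule in SAP 14.3.3 screens for givinostat only: "No current treatment with givinostat (Duvyzyat®) (Variables: other\_meds\_listed ≠ “givinostat,” “duvyzyat". Leaving SGLT2 users in that pool is consistent with Protocol 7.4, under which "sodium glucose cotransporter-2 (SGLT2) inhibitors, are permitted during the OLE". The open-label baseline is Month 12, so a baseline SGLT2 covariate could not balance use that trial subjects start afterwards.

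**Conclusion.** The point holds for the DB matching. The rule in SAP 14.3.2 does not do what its own criterion says: two of the three SGLT2 generic strings match no correctly spelled entry, and no later step named in the SAP removes or balances the subjects who pass.

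The error in the text is certain. Its effect on the results is conditional on three things: the rule being programmed literally, the field holding the correctly spelled generic name, and at least one NH subject taking empagliflozin or canagliflozin. For the matched comparison, that subject must also be selected. The effect could be zero, and its direction cannot be predicted. The randomised comparisons and the primary safety endpoint are not touched. It should be corrected because the correction is cheap and the criterion is the sponsor's own.

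**What to change.** In SAP 14.3.2:

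1. Change the two strings to empagliflozin and canagliflozin, as in the prose.
2. State that the search ignores case and looks for each name within the entry, or that it runs on coded drug names.
3. If the present spellings are genuine data-entry variants, keep them beside the correct ones, as Table 1 does for steroids.
4. Review all unmatched `other_meds_listed` entries by hand before matching.

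SAP 14.3.2 opens by saying that NH subjects were selected, in the past tense, so the program should be checked in case the screen has already been run.

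The cost is a corrected list of terms and one review of unmatched entries. A few NH subjects may leave the eligible pool.

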7.3.1 Inclusion Criteria

Individuals who meet all of the following criteria are eligible for enrollment as study subjects:

1. Males 7 years of age and older with the diagnosis of DMD, defined as phenotype consistent with DMD and either positive genotype, first degree relative with positive genotype, or confirmatory muscle biopsy.
2. Stable dose of oral corticosteroids for at least 8 weeks or has not received corticosteroids for at least 30 days.
3. Stable cardiac function defined as change in LVEF of < 15% and no heart failure admission over the last 12 months; LVEF 35% or greater by cine CMR or echocardiography; myocardial damage in one or more left ventricular segments evident by late gadolinium enhancement allowed; concurrent angiotensin-converting enzyme inhibitors (ACEI), beta-blocker (BB) or angiotensin receptor blocker (ARB) therapy allowed (selection of which dictated by clinical care) if started three months or greater from first dose of IMP without change in dose. Aldosterone receptor antagonists (e.g. spironolactone or eplerenone) allowed if started 12 months or greater from first dose of IMP. No changes throughout the study allowed except in the event of a decline in left

ventricular ejection fraction (LVEF) >5% following the baseline CMR as measured by a subsequent CMR at the same center. Should this occur, changes in cardiac medications are allowed on study, and the patient may remain on IMP.

- a. **Late-stage cohort:** Subjects are eligible for the late-stage cohort if the subject has:
 - i. LVEF 35%-45% by cine cardiac magnetic resonance imaging (MRI) or echocardiography or
 - ii. historically documented LVEF 35%-45% by cine cardiac magnetic resonance imaging (MRI) or echocardiography and if their baseline MRI is less than 50%.
4. Subjects aged 18 years and older, informed consent obtained directly. For subjects ages 7–17 years old (yo), both assent from the subject and permission from a parent or guardian.
5. AAV-based gene therapy permitted if ≥ 2 years from AAV administration and subject has documented cardiac decline defined as >5% decline in LVEF over a 2-year period following AAV administration using consecutive CMRs or echocardiography performed at the same center (must still meet inclusion criterion #3).

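### Natural-history controls are barred for any past heart failure and face no LVEF-stability rule, whereas trial subjects face time-limited heart-failure rules and a stability rule

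*SAP*

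**What the plan says.** SAP 14.3.2 describes its list of NHS filters by their purpose: "Subjects from the NH were selected to reflect the baseline criterion of the CPI-IFE007 study before the propensity score is calculated". Two items on the list bear on cardiac history. One is "Subjects with no history of heart failure". The other is "2 years data of LVEF", which asks that measurements exist but limits nothing about how they changed. SAP 14.3.3 carries both items into the open-label matching, where Month 12 serves as baseline.

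The trial's own rules are in two places. Protocol 7.3.1, criterion 3, requires "Stable cardiac function defined as change in LVEF of < 15% and no heart failure admission over the last 12 months". Protocol 7.3.2, criterion 4, excludes subjects who "Require antiarrhythmic therapy and/or initiation of diuretic therapy for management of acute heart failure in the last 6 months". Neither is a lifetime exclusion.

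**The concern.** Matching balances only what is in the propensity model. An eligibility filter acts before that step, so if it differs between the two sources, the groups can differ on factors that matching never sees. There are two such differences here.

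- **Heart-failure history.** A boy with an older event, or with heart failure managed without a recent admission or acute treatment, may enter the trial on these criteria but cannot be a control. On clinical reasoning this would tend to leave healthier controls and work against the drug.
- **LVEF stability.** A boy whose LVEF changed by 15% or more in the past year is kept out of the trial but may be a control. This can admit faster decliners and work in favour of the drug.

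At stake is the reading of every NHS-based efficacy result. The open-label extension depends on it most, because it has no concurrent control.

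**Working it through.** No figure in the plan needs reproducing; the check is a comparison of texts.

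| Rule | Trial subjects | NHS controls (SAP 14.3.2, 14.3.3) |
|---|---|---|
| Heart-failure admission | Barred if within 12 months (Protocol 7.3.1) | Barred at any time, as part of any history |
| Antiarrhythmic therapy and/or new diuretic for acute heart failure | Barred if within 6 months (Protocol 7.3.2) | No separate rule; covered only so far as it counts as history |
| Older or non-admitted heart failure | Not in itself a bar | Barred; term not defined |
| LVEF change under 15% | Required | Absent |
| LVEF floor | 35% | 35% (in 14.3.2, "baseline is pre-dose in study") |

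The floor agrees. The heart-failure and stability rows do not.

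**Does anything else supply the missing rules?**

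1. *NHS eligibility.* Protocol 11.5 describes it as broad and resting on the DMD diagnosis, so it brings no stability rule.
2. *Propensity model.* SAP 14.3.4 lists age, baseline LVEF, background DMD drugs and cardiac drug classes. It has no term for heart-failure history or for prior LVEF change. Diuretic use, a partial proxy, is a covariate in SAP 4.5.1 but is missing from the 14.3.4 list to which 4.5.1 refers.
3. *Sensitivity analyses.* SAP 14.3.8 plans weighting, a 0.2 caliper, exact matching and a comparison with the whole eligible cohort before matching. That cohort has already passed the filter, and none of the analyses is described as changing it.

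**Open-label extension.** Protocol 8.1.3 makes completion of 12 months of treatment the condition for entry and describes no heart-failure rescreen. Protocol 7.4 lets a subject whose LVEF has fallen by more than 5% stay on study drug. A trial subject with a heart-failure event during the double-blind year could therefore reach the extension, while an NHS subject with the same course is filtered out. The mismatch is wider here than in the double-blind period.

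**Illustration of sensitivity (assumed inputs, not an estimate).** Take 16 high-dose subjects against 16 placebo plus 32 NHS subjects (2:1, no dropout), with normal data, unit SD and no drug effect. Let the NHS mean change differ from placebo by s SD. The pooled control mean then moves by (16 × 0 + 32 × s)/48 = 2s/3. Two-sided Wilcoxon tests at 0.05, with 10,000 simulated trials per row, gave:

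| Size of s | Pooled shift, 2s/3 | Rejection rate |
|---|---|---|
| 0 | 0 | 5.1% |
| 0.2 | 0.13 | 7.0% |
| 0.3 | 0.20 | about 10% |
| 0.5 | 0.33 | 19.1% |

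The excess falls almost wholly on one side. With NHS subjects doing worse by 0.3 SD, 9.6% of trials falsely favoured the drug and 0.4% falsely favoured control. With NHS subjects doing better by 0.3 SD, 9.3% falsely favoured control and 0.5% the drug. In the open-label comparison no placebo group dilutes the shift, so all of s passes through rather than two thirds of it.

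**The case against.** The strongest reply is that the consequence is limited. The primary endpoint is safety, SAP 4.5.3 labels the NHS comparisons supplementary, and the randomized comparisons do not use these controls. That stands for the double-blind period. It carries less weight for the extension, where the Protocol synopsis names the NHS as primary comparator.

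Baseline LVEF, age and cardiac drugs are also partial proxies for heart-failure severity. That stands too, but they do not record a past event or a recent fall in LVEF. The absence of a caliper in the main matching could worsen matches in a thinned pool; the planned 0.2-caliper analysis partly answers this, though it leaves the filter as it is.

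The two differences may offset each other. They may, but neither is measured, so this is no safeguard.

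Three stronger readings are tempting and are not supported:

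- *That the 12-month admission rule is the trial's only heart-failure restriction.* Exclusion 4 adds a 6-month rule. This narrows the gap but does not close it, since both windows are finite.
- *That the controls are biased in a known direction, or that a stated share of the pool is lost.* The documents do not count NHS subjects with a heart-failure history, NHS subjects with unstable LVEF, or enrolled subjects with older heart failure.
- *That the harm falls on the advanced-stage half of the whole trial.* No passage shows where NHS heart-failure histories cluster, and double-blind matching is to the high-dose arm only, with 8 of 16 subjects planned as advanced stage.

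**Conclusion.** The concern holds within these limits. By their own stated aim, SAP 14.3.2 and 14.3.3 should mirror trial entry. Instead they apply an unlimited, undefined heart-failure exclusion and omit the LVEF-stability rule. Nothing later in the plan restores either rule or tests the effect of the filter.

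The net bias has unknown sign, and the documents do not allow its size to be derived; the simulated rates show only what an assumed shift would do. That the two factors predict further decline is clinical reasoning, not a figure in the documents. The double-blind NHS comparison and, more importantly, the open-label comparison are affected. The change should be made before those results are interpreted, but it does not threaten the randomized analysis.

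**What to change.** **SAP 14.3.2.** Replace the no-history line with the trial's own time-limited criteria, meaning both inclusion 3 (12-month admission) and exclusion 4 (6-month treatment for acute heart failure), applied at the NHS index visit as far as the data allow. Using inclusion 3 alone would create a new mismatch. Apply the LVEF-change-under-15% rule to NHS subjects who have an earlier yearly visit, at least as a sensitivity analysis.

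**SAP 14.3.3.** Anchor the same entry rules to the NHS visit that corresponds to trial entry, one year before the Month 12 index. Applying them at Month 12 would impose on controls a screen that open-label subjects never face.

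**If the data fall short.** Protocol 11.5 says the NHS collects medical history and concomitant medication, but neither document shows that heart-failure events are dated. If they are not, say so, define what counts as a history of heart failure, list the trial criteria that cannot be applied, and add a sensitivity analysis imposing the same no-history rule on trial subjects and controls alike. The trial collects medical history (Protocol 8.1.1, SAP 5.4).

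**Cost.** SAP wording, some programming and a re-run of the filter and matching. The stability analysis will use a smaller pool, because it needs one yearly NHS visit before the entry-equivalent visit; for the open-label matching that visit lies two years before the index.
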